To evaluate the impact of the game in this Phase II study, we will conduct a randomized controlled trial (RCT) enrolling 200 clients randomized to *OTG* or a control condition of *RVs* in a 1:1 ratio. We will recruit these participants from OnTrackNY's Early Intervention for Psychosis (EIP) clinical centers after screening for eligibility. After consent and initial interview (baseline), participants will be randomly assigned to either *OTG* or *RV*. Following an intent-to-treat framework, we will then assess each client participant at 2 additional time points regardless of participation in their assigned condition: post-intervention at 2 months and follow-up at 5 months after baseline. Ten clinicians working with these clients will also be recruited for semi-structured key informant qualitative interviews. Our rationale for selecting a randomized controlled design stems from our Phase I findings, which suggest that the game may be effective in addressing young people's hopefulness, stigma, and understanding around first episode psychosis. An RCT design will allow us to examine how specific aspects

of the game impact outcomes in these areas, as compared to more static, passive online resource.

Subjects, Sampling, and Recruitment

Subjects

OnTrackNY is New York State's coordinated specialty care (CSC) program. Funded by state dollars, a SAMHSA Healthy Transitions Grant, and Mental Health Block Grant funds, the state currently supports 13 teams throughout the state. Eight additional programs are expected to come on line within the next 6 months. The program serves young adults ages 16 to 30.

At the time of funding, we expect 14 CSC sites to be located in downstate New York. Although sites will have different numbers of clients (20–40), approximately 450 clients will be participating in the program at that time. Based on the 2-year program, approximately 225 new clients will start the program during the year of recruitment. Based on our previous experience, we believe we will be able to recruit 33% of the eligible clients. If for some reason, we fall short of our recruitment goals, we will use the other OnTrackNY sites until we meet our goal. We anticipate no challenges in recruiting clinicians (n=10).

Sampling

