the RA clarifies points of confusion then re-administers the questionnaire. Clients again failing to answer questions correctly will not be consented into the study. Purposive sampling will be used to recruit clinicians for semi-structured interviews.

We have extensive experience maintaining participant engagement and contact during intervention studies. Once enrolled, we ask participants to complete a contact information form that we have found effective in other studies for maintaining communication and participant retention. It requests multiple ways to reach the person (phone, email, letter) and people of the participant's choosing we may contact if the primary methods of contact are unsuccessful, preferences around communication details (such as whether we may leave a voice message on a given phone number and with what specificity), and signed confirmation that we have permission to use the information for study communications. Study staff then make reminder calls/texts prior to each study activity (assessment, group meeting, individual consultation) throughout the study. These contacts serve to remind participants of the meetings, to answer questions, help avoid or resolve attendance obstacles, and maintain a high level of positive mutual engagement. Study staff also engages in active outreach if/when participants miss a study activity. Based on our previous work and the timeframe of the follow-up assessments, we estimate 10% attrition at 2 months and 20% attrition at 5 months.

Study Conditions

Clinicians will be oriented to both study conditions (the game and the website) via a brief (15-minute) presentation that will also be available as an online video. For all study participants, we will request clinicians make 3 simple inquiries with respect to viewing the videos/information on the website or playing the game: Have you had a chance to look at the website/play the game in the last week? Was it helpful? Is there anything you want to talk about? Potential follow-up questions will also be discussed with clinicians. From this pool of clinicians, we will recruit 10 to participate in semi-structured interviews on their experiences in working with clients participating in each study condition (e.g., observations of changes in attitudes toward treatment, self-efficacy, a sense of hope, treatment engagement, and stigma).

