Following informed consent, the RA will open the envelope indicating to which intervention the participating client was randomized. For people in the *OTG* condition, the RA will review an outline of the game, provide directions on how the game works, and reiterate the expectation that the participant will finish the game in the following 2 months, if not sooner. We expect that spending 1 hour a week playing the game will be sufficient to complete all levels of the game. For participating clients in the *RV* condition, they will be reminded that they are expected to view the recovery videos and download the information materials from the website. We anticipate that the materials could be viewed in approximately 4 hours. The RA will remind the participant that they will receive an email with a link to either the game or the website, depending on their study condition. All participants will be provided with an email address and telephone number. If a participating client does not open the email with the link for 2 weeks, another email will be sent.

Intervention Description (OTG)

The intervention condition will consist of 2 components: (1) provision of the game to the participating clients via an email link, and (2) brief interactions with their mental health provider with respect to reactions they may have when playing the game. Components of the game are described in the *Innovation* section of the proposal. The participant will be reminded via email once a week to play the game/visit the website for a period of 2 months. After that time,

reminders to play the game/visit website will no longer be sent, but the participant may continue to play if they wish.

Control Condition (RV)

The control condition will consist of access to a website that will contain the recovery videos and the static information that is contained in the game. In the control condition, mental health providers will also ask about possible reactions to viewing the recovery videos and information on the website. At the end of the study (after the follow-up assessment), the *RV* participants will be provided access to the game. The table below shows how the conditions align.

Component	OnTrack>The Game (OTG)	Recovery Videos Website (RV)
1. Testimonials of Hope and Recovery	Movie theater zone with 20 brief (3–5 minute) video interviews with young adults who have experienced psychosis.	Online library of the 20 video interviews from OTG

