Client interviews: A subset of 10 clients from each study condition (n=20) will be asked to participate in semi-structured interviews after using *OTG* or *RV*. Questions will explore their experiences in using the product (navigation and access, preferences, facilitators and barriers to use); attitudes toward treatment and working with their clinician; and their feelings of self-efficacy, recovery, hope for the future, and stigma. Clients will receive \$25 for participating in these interviews.

Clinician interviews: Ten clinicians, working with clients from both study conditions, will also be asked to participate in semi-structured interviews to explore their experiences in working with clients from each condition and changes in attitudes they may have observed, barriers and facilitators to use of each product, and feedback on the product components. Clinicians will receive \$50 for participating in these interviews.

We feel that the number of interviews described will be sufficient to reach data saturation, but we will add interviews if needed.

Quantitative: Baseline, post, and follow-up surveys will be completed with each study participant via in-person interviews using direct data entry into a secure online database built with Qualtrics software. Baseline assessment will occur at the time informed consent is obtained if possible, and at this time we will ask participants for demographic data including age, gender, race and ethnicity, education level, relationship/marital status, work, and school participation. Data on treatment engagement will be extracted from clinic charts.

The following table presents domains, measures, and time-points for administering them.

Quantitative Measures and Frequency of Assessments by Specific Aim				
Domain	Measure	Administered at study time-point		
		BL	Post	Follow-up
Aims 2 and 3				
Stigma Concerns	Rüsch Stigma Stress	x	x	x
	Questionnaire on Anticipated Discrimination			
Empowerment	Recovery Attitude Questionnaire (RAQ)	x	x	x
	Roger's Empowerment Scale Total			
	Herth Hope Index (HHI)			
Treatment Engagement	Singh O'Brien Level of Engagement Scale (SOLES)	x	x	x

	Number of unduplicated visits during the follow-up period is above engagement threshold			x
Description of Sample and Potential Moderators and Mediators				
Participant Demographics	Demographic Form/Chart Review	x		
Experience with Game Functionality and Design	EGameFlow		x	x
Use of Game/Website	Springroll Learning Module/Google Analytics		x	x

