Data Analysis

All data will first be screened for errors via frequency and contingency tables and univariate and bivariate plots. These will also allow us to check for missing data and that variable distributions are compatible with the statistical models we will use.

Triangulation increases confidence in the validity of a finding if it converges across disparate sources of information. Qualitative data will be triangulated by sources (comparing client and clinician interview data). Further, the research team will also actively work to integrate quantitative and qualitative datasets, comparing results during and after analysis, to allow for ongoing interpretation.

We will use a mixed-effects, 2-level model (SAS Proc Mixed, GLIMIX) to test primary hypotheses with a random class effect to account for intra-team correlation (ICC). The longitudinal assessments (baseline (t=1), post-treatment (t=2), and 6-month follow-up (t=3)) will be nested within participants and participants nested within teams. Adjustment for baseline response will reduce residual variation at t=2 and t=3 resulting in greater power. Correlation in the response at t=2 and t=3 (conditional on response at t=1) will be modeled by allowing the corresponding error terms to be correlated rather than using a random individual effect. That is, we will use a hybrid model with both a random class effect and correlated error terms (conditional on baseline value and the class effect).

Quantitative Analysis

Aim 2: A Generalized Linear Mixed Model will be used with the outcome measures listed above as the dependent variables and treatment group (*OTG* vs. *RV*) as the independent variable of interest. Baseline outcome measures and any covariates determined from preliminary analyses will also be included in the model. Post hoc analyses will include assessment of treatment group differences in the outcome measures at post-intervention and 3-month follow-up. Engagement will be binary variable; therefore a log link will be employed. The test of hypothesis 1 and 2 will operationally be the test of whether the coefficient of the *OTG/RV* condition term is significantly greater than zero (2-sided test) for each contrast.

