Clients may feel uncomfortable disclosing their mental health status to researchers. There is possible risk of coercion, mainly from the incentives that participants may be offered in the different research activities. The likelihood of this risk is low because compensation is commensurate with the amount of time required to complete this study. We will also specify in the consent form and consenting process that participation in this study is voluntary and the decision to participate in this study will not impact services received or staff employment. There is no greater risk associated with the comparison condition. The research team will clearly describe this risk and stress the importance of respecting the confidentiality of all participants. All study personnel will have successfully completed and/or updated their human subject's protection certification and will be trained on keeping data secure and participant information confidential. The benefits of this study far outweigh the minimal risks to study participants.

Safeguards are critical for clients, who will be sharing personal information about their mental health experiences. Safeguards will be put in place with participating programs in the event that a client experiences any form of distress, and immediate clinical support will be made available should it be necessary. This is the practice used in Phase I of the study and is always used when C4 staff work with individuals with mental health challenges. All participants will be reminded that participation is voluntary and that they can withdraw from the study at any point without reason or penalty. Once again, our primary concern is that we do no harm in working with clients during our study and that we take every precaution to avoid risk. This is why our team carefully considers inclusion/exclusion criteria and ensures that we are regularly attending to these criteria. The research team will work closely with the site liaisons, checking in regularly to ensure that it is appropriate for clients to continue to participate. Any concerns will be addressed at that time, and, as appropriate, the liaison and/or member of the research team will reach out to the client directly if deemed appropriate by their treatment team. If the team feels that clinically it is not in the best interest of the client to continue, we will discontinue the study with that individual.

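### Clinical discontinuation ends the whole study for a client, which conflicts with the commitment to assess everyone at 2 and 5 months and, read literally, also drops the chart-based engagement outcome (minor)

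*Combined protocol and SAP*

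**What the plan says.** Two rules bear on a client who stops.

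- **Research Design** sets an intent-to-treat follow-up: "we will then assess each client participant at 2 additional time points regardless of participation in their assigned condition".
- **Potential Risks** has site liaisons check regularly that participation is still appropriate. If continuing is judged clinically unwise, "we will discontinue the study with that individual".

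Outcomes come from two sources. Under Data Collection, "Baseline, post, and follow-up surveys will be completed with each study participant via in-person interviews", and separately "Data on treatment engagement will be extracted from clinic charts". The chart outcome is whether the visit count during follow-up exceeds a threshold.

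Staff can know the arm. Under Study Conditions, "we will request clinicians make 3 simple inquiries with respect to viewing the videos/information on the website or playing the game", and after consent "the RA will open the envelope indicating to which intervention the participating client was randomized".

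On missing data, Recruitment says "we estimate 10% attrition at 2 months and 20% attrition at 5 months", without saying whether clinical discontinuations are included. Data Analysis gives no handling for these clients beyond the model itself: "Correlation in the response at t=2 and t=3 (conditional on response at t=1) will be modeled".

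**The concern.** The two rules give different answers for the same client. One follows everyone; the other ends the study for clients selected on clinical grounds by staff who can know the arm. If such removals differ by arm, the clients analysed are no longer the clients randomized, and the intent-to-treat comparison is weakened.

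The chart outcome is where the loss is least justified. Engagement with the program is named in Hypothesis 2, and treatment participation is the outcome of the Aim 3 mediation analysis. Potential Risks first names discomfort in disclosing to researchers. That is a reason to stop interviews, but not to stop reading a clinic chart.

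A difference in removal by arm is plausible but not shown. Only the game includes role-play of difficult situations, and one trial-level stopping reason is destabilization among clients using the intervention. Yet the plan expects no medical or psychological risk from either condition.

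Existing oversight does not settle the point. The team reviews retention and the DSMB is consulted on significant data loss, but neither provision asks for clinical discontinuations, or their reasons, by arm.

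**Working it through.** **Text.** For the 2- and 5-month assessments, Research Design says continue and Potential Risks, read literally, says stop. This is a conflict. For chart extraction, Data Collection names the source but no visible section says whether extraction continues after discontinuation. Only the literal reading of Potential Risks implies that it stops.

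**Size.** The plan has no figure to reproduce. From the documents: 200 clients, 1:1, 20% attrition at 5 months, so 100 × 0.80 = 80 per arm; two-sided tests. Assumed: 5% alpha (not stated), removal rates, outcome gaps, correlations, other attrition unrelated to outcome, team clustering ignored.

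*Scales at 5 months, removal before 2 months, no baseline gap.* With r the share removed and d the SDs by which removed clients fall below their arm mean:

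shift = d × [r_OTG/(1 − r_OTG) − r_RV/(1 − r_RV)]

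| Removed, OTG and RV | Calculation at d = 1 | Shift, d = 1 | Shift, d = 0.5 |
|---|---|---|---|
| 2% and 1% | 0.0204 − 0.0101 | 0.010 SD | 0.005 SD |
| 5% and 2% | 0.0526 − 0.0204 | 0.032 SD | 0.016 SD |
| 8% and 2% | 0.0870 − 0.0204 | 0.067 SD | 0.033 SD |
| Equal rates | | 0 | 0 |

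*Removal after 2 months.* The planned model uses the 2-month value. With correlations of 0.5 (baseline with each later visit) and 0.6 (2 with 5 months), the slope of the 5-month on the 2-month value given baseline is (0.6 − 0.25)/(1 − 0.25) = 0.467. If the full shortfall is already present at 2 months, the shift is multiplied by 1 − 0.467 = 0.533; at d = 1 this gives 0.005, 0.017 and 0.035 SD. If half is present, the multiplier is 1 − 0.233 = 0.767, and the 8% and 2% case gives 0.051 SD. A client removed before 2 months contributes only a baseline value.

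*Against the standard error.* Unadjusted, √(2/80) = 0.158 SD; baseline-adjusted, 0.158 × √0.75 = 0.137 SD.

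- 8% and 2%, d = 1: 0.0665/0.158 = 0.42, type I error 7.0%; 0.0665/0.137 = 0.49, type I error 7.8%.
- 2% and 1%, d = 1: 0.0103/0.158 = 0.07, type I error 5.05%.

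*Chart engagement, only if extraction stops.* With true engagement 70% in both arms and a proportion q engaged among removed clients, the analysed rate is (0.70 − r·q)/(1 − r). For 8% and 2%:

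- q = 0.5: 0.660/0.92 − 0.690/0.98 = 0.717 − 0.704 = +1.3 points
- q = 0.7: 0
- q = 0.9: 0.628/0.92 − 0.682/0.98 = 0.683 − 0.696 = −1.3 points
- q = 0.2 (pessimistic): 0.684/0.92 − 0.696/0.98 = 0.743 − 0.710 = +3.3 points

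For q between 0.5 and 0.9, the other cases stay within 0.6 points (5% and 2%) and 0.2 points (2% and 1%). Charts do not depend on interview attendance, so the standard error rests on the 92 and 98 remaining charts: √(0.21/92 + 0.21/98) = 6.7 points. A shift of 1.3 points is 0.2 standard errors; 3.3 points is 0.5.

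**The case against.** The strongest case is that this is a wording tension around a legitimate safeguard, with no demonstrated harm.

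- **A reader might infer that the plan is silent on the 2- and 5-month assessments.** It is not. Research Design commits to them for every client. The fault is that the discontinuation rule contradicts that commitment. The silence concerns chart extraction only.
- **Terms for later data use may exist elsewhere.** The consent pages were not available, and post-discontinuation data use is a natural topic for them. This stands. If the terms are there, a cross-reference is enough.
- **Stopping research contact is defensible** for clients with early psychosis, some of them minors. This stands for the interviews, so the treatment team should keep that option. It does not reach chart extraction, which needs no contact.
- **Removals may be few.** No risk is anticipated in either condition. An 8% rate would be 8/20 = 40% of an arm's expected 5-month attrition, and such a pattern, if it reflected destabilization, could itself prompt the plan's stopping criterion. This stands, and it is why the upper cases above are bounds and not expectations.

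**Conclusion.** The point holds as a minor one. The discontinuation rule conflicts with the intent-to-treat follow-up and, followed literally, loses an outcome that could be kept without contacting the client.

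The bias is probably small. Under the main assumptions it runs from under 0.1 standard errors (2% and 1% removal) to about 0.5 on the scales (8% and 2%, a full SD worse, all before 2 months). For chart engagement it is 0.2 standard errors at 8% and 2% removal, or 0.5 if only a fifth of removed clients are engaged. It vanishes if removal rates and shortfalls are equal in the two arms. Every rate, gap and correlation here is assumed.

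A reader might infer that the trial's comparison is seriously compromised, or that the rule would favor the game. The documents support neither: they give no removal rate, no imbalance and no direction. Nor is this a point about safety detection. The case for change rests on low cost, and on the fact that interviews missed after removal cannot be recovered.

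**What to change.** Leave the clinical decision with the treatment team, including the option to stop interviews, and add four statements:

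1. Clinical discontinuation stops the product and the reminders.
2. Chart-extracted engagement continues and is analysed in the assigned arm unless consent is withdrawn.
3. The 2- and 5-month assessments follow the Research Design commitment unless the treatment team judges the assessment itself unsuitable for that client.
4. Clinical discontinuations, with reasons, are reported by arm.

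For the chart outcome this removes the selection except where consent is withdrawn. For the scales it reduces the selection and makes the remainder visible, because the treatment team still decides.

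The cost is protocol and consent wording, continued chart access, and some contact for clients who remain suitable for assessment. No visit is added beyond those already planned.
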